**Distance And Intermediate Visual
Acuity After Phacoemulsification
Using A New Generation
Monofocal Intraocular Lens
Compared To Standard Monofocal
Intraocular Lens**

NCT05430295

Date:2-9-2022

Cairo University

KASR ALAINY
CAIRO UNIVERSITY - FACULTY OF MEDICINE

Faculty of Medicine, Cairo University Postgraduate Research Protocol Template

1. Study

- a- Proposed Study Title: Distance And Intermediate Visual Acuity After Phacoemulsification Using A New Generation Monofocal Intraocular Lens Compared To Standard Monofocal Intraocular Lens .
- b- Degree : Masters of ophthalmology.
- c- Date of Registration MSc or MD: October 2019.

3. Scientific committee approval

(Was it scientifically approved by the department?) Yes

Date of approval:

4. Background and Rationale:

Cataract surgery is the most commonly performed surgery of the eye and monofocal intraocular lenses are the most widely used intraocular lenses. With the aspheric technology using the aspheric intraocular lenses like TECNIS 1-piece (Johnson & Johnson Vision, Santa Ana, CA, USA) can provide negative spherical aberration and results in better contrast sensitivity and visual quality ^{(1),(2)}.

Standard monofocal lenses only allow the patient's vision to focus at one distance (i.e. distance or near), thus patients receiving monofocals often require glasses after surgery to improve their near and/or intermediate vision.

Multifocal lenses are designed to split incident light into two or more points of focus, but these lenses are limited by the demands of minimizing optical aberration and balancing the focused and out -of -focus images ⁽³⁾

Multifocal IOLs are diffractive IOLs and are known for dysphotopsia (including glare and halos) that can negatively impact the quality of vision ⁽⁴⁾.

Cairo University

KASR ALAINY
CAIRO UNIVERSITY - FACULTY OF MEDICINE

In contrast to monofocal and multifocal IOLs, EDOF lenses e.g Symphony IOL (Johnson & Johnson Vision, Santa Ana, CA, USA) are IOLs that provide an extended range of focus above a defined functional visual acuity threshold to provide useful distance and intermediate vision.

Therefore, EDOF lenses should provide functional vision over a range of distances while ideally reducing the incidence of “bothersome” halos or glare which offer advantages to accommodate the patient’s lifestyle ⁽⁵⁾.

The new Tecnis® Eyhance IOL (model ICB00, Johnson & Johnson Vision, Santa Ana, CA, USA), It is claimed to be an effective option for patients regarding better intermediate visual acuities relative to the standard monofocal intraocular lenses. It is a refractive modified monofocal lens with 0.50 D of additional power in its central 2-mm zone featuring a continuous change in power from the periphery to the center of the lens, creating a unique anterior surface that improves intermediate vision, maintains distance image quality comparable to aspheric monofocal IOLs, with similar profile of photic phenomenon and keeps on reducing spherical aberration close to zero ⁽⁶⁾.

Considering the marginal price difference between the new Eyhance lens and the Tecnis monofocal aspheric lens, and the potential additional benefits of improving the intermediate distance vision while preserving the optical quality and minimal photic phenomena ⁽⁷⁾, we believe that proper study of the outcomes of using this lens could influence our choice of monofocal intraocular lenses in cataract patients. Hence, the objective of the study is to evaluate the distance, intermediate visual acuities, assess contrast sensitivity and photic phenomena, in patients undergoing cataract extraction with implantation of Tecnis® Eyhance (model ICB00, Johnson & Johnson Vision, Santa Ana, CA, USA) or Tecnis® 1-piece (model ZCB00, Johnson & Johnson Vision, Santa Ana, CA, USA) ^{(8),(9)}.

5. Objectives:

- 1- Comparison of uncorrected and best corrected distance and intermediate vision in patients whom implanted with monofocal TECNIS Eyhance ((model ICB00) or TECNIS 1-piece (model ZCB00) IOLs after phacoemulsification.

Cairo University

KASR ALAINY

CAIRO UNIVERSITY - FACULTY OF MEDICINE

- 2- Evaluation of contrast sensitivity between the two patient groups.
- 3- Evaluation of photic phenomena.

6. Study Design:

- Descriptive: - Survey (cross sectional)
- Qualitative
- Analytic: - Observational: - Case-control study
- Cross sectional analytic study
- Cohort (Longitudinal) study
- Experimental: - Randomized Clinical Trial Phase:
- Non-randomized clinical trial
- Animal study
- Cellular study
- Others: Please describe: **Prospective case series**

7. Study Methods

- Population of study:

Patients undergoing cataract surgery and implantation of monofocal intraocular lens
Tecnis® Eyhance 1-piece
Or Tecnis® 1-piece

Cairo University

KASR ALAINY
CAIRO UNIVERSITY - FACULTY OF MEDICINE

- Study location:

Kasr Alainy & Eyecare center, Maadi, Cairo.(ETDRS chart, Pelli Robson illuminated chart, OPD scan being not available at Kasr Alainy hospitals).

- Inclusion criteria:

- Patients aged more than 50-75 years old undergoing cataract surgery.
- Preoperative corneal astigmatism equal to or less than 0.75 D.

- Exclusion criteria:

- Other ocular comorbidities such as glaucoma, corneal opacities, chronic or recurrent anterior uveitis, diabetic retinopathy, age -related macular degeneration.
- Previous ocular surgeries.
- Undergoing combined surgeries.

Methodology in details:

40 eyes of 20 patients will be included in this prospective study. The Tecnis® Eyhance IOL will be implanted in 20 eyes of 10 patients (group 1), and 20 eyes of 10 patients will be implanted with Tecnis® 1-piece (group 2).

Preoperative assessment:

All selected patients will receive thorough explanation of the study design and aims, and an informed consent will be obtained from all patients.

Eyes before intervention will be subjected to:

- Measurement of uncorrected and best-corrected distance visual acuity using ETDRS chart.
- Slit lamp examination.
- Measurement of intraocular pressure using applantation tonometer.
- Dilated fundus examination using binocular indirect slit lamp biomicroscopy.
- Specular microscopy .

Cairo University

KASR ALAINY
CAIRO UNIVERSITY - FACULTY OF MEDICINE

- Optical biometry using (IOLMaster 500; Carl Zeiss Meditec AG, Jena, Germany) and using online Barrett's universal formula. With target refraction of 0 or +0.25 D in the Eyehance group While in the Tecnis group the dominant eye will be aimed at 0 D and the non-dominant eye for -0.5 D.

Surgical intervention:

Surgery will be performed under topical anaesthesia using topical Benoxinate or local anaesthesia using peribulbar Lidocaine injection.

- Speculum used to maintain lids open.
- Clear corneal incision placed superotemporally using 2.2 mm keratome and paracenteses are placed using 15 superblade at 90 degrees to the main wound.
- Followed by formation of anterior chamber using Ophthalmic Viscoelastic Device (hydroxypropyl methylcellulose).
- Continuous curvilinear capsulorrhesis is created using straight sharp tipped Uttrata's capsulorrhesis forceps aiming at 5 mm size.
- Phacoemulsification of nucleus
- Bimanual irrigation and aspiration of cortical material.
- Injection of Ophthalmic Viscoelastic Device to form anterior chamber and inflate the capsular bag.
- Implantation of Eyehance or Tecnis® 1-piece intraocular lens in capsular bag.
- Irrigation and aspiration of Ophthalmic Viscoelastic Device.
- Injection of intracameral moxifloxacin in the capsular bag and hydration of self-sealing clear corneal incisions.

Post-operative:

All patients will receive a topical antibiotic (moxifloxacin) and steroids (Prednisolone acetate) eyedrops in a slow tapering course over 4 weeks.

Follow up:

Cairo University

KASR ALAINY

CAIRO UNIVERSITY - FACULTY OF MEDICINE

All patients will be examined at day 1, 1 week and 1 month and 3 months postoperative.

At three months follow up all patients will be evaluated regarding:

- Corrected and uncorrected distance (at 6 meters) and intermediate (at 66cm) vision both unocular and binocular.
- Photopic contrast sensitivity using Pelli Robson chart illuminated chart with controlled ambient illumination
- Mean binocular defocus results will be measured and defocus curves of the two lenses will be created.
- A questionnaire to evaluate the photic phenomena and spectacle independence will be explained and filled by the patients.

Distance visual acuities will be examined by ETDRS chart and intermediate and near visual acuity by Jaeger chart at 66 cm and 33 cm respectively

Measured values of the visual acuity will be expressed in decimal values and will be converted to logMAR values.

- **Intervention:**

- Diagnostic intervention (please describe):
- Therapeutic intervention (please describe): phacoemulsification, Eyhance IOL or TECNIS 1-piece IOL implantation.
- No intervention

Both diagnostic and therapeutic.

- **Does the research involve?**

- Human participants

Cairo University

KASR ALAINY
CAIRO UNIVERSITY - FACULTY OF MEDICINE

Biological samples/Tissues

Identifiable private data/Information

- **Type of consent of study participants:**

Written consent
 Oral consent
 No consent needed (Please justify)

- **Potential risks:**

(Please mention all risks involved even mild ones as pain, discomfort, chance of infection or psychological effects)

- 1- Risks related to surgical intervention including corneal oedema, infection, retinal detachment, hemorrhage, IOL displacement, elevated intraocular pressure, optic atrophy,
- 2- Risks related to intraocular lens including photic phenomena as halos and glare.

- **Confidentiality of data:** will be maintained in a secure file with the investigators.

9- Study outcomes:

- **Primary outcomes** (Most important measurable outcomes)

Uncorrected and best-corrected distance, and intermediate visual acuity.

Cairo University

KASR ALAINY
CAIRO UNIVERSITY - FACULTY OF MEDICINE

- Secondary outcome parameters (other outcomes to be assessed)

- 1) contrast sensitivity.
- 2) Photic phenomena.
- 3) Spectacle independence.

10- Sample size (number of study subjects included and justification including the clinical and statistical assumptions supporting sample size calculation)

With a sample size of 18 (9/group), we will have a power of 95% to assess whether the mean logMAR For UIVA is significantly lower in the new monofocal IOL (~0.16 +/-0.06) compared to the standard monofocal IOL with a mean logMAR for UIVA Of ~0.27 (0.06), using a 2 samples means test and a significance level of 0.05

11- Statistical analysis (Please describe your data analysis plan)

Statistical plan

Summary statistics will be done, categorical variables would be presented as frequency and percentages and numerical ones as mean (SD) or median (IQR) as appropriate.

Comparison between the two groups will be done using the Students t test or the Wilcoxon rank sign test according to data normality. The Chi squared test will be used to compare categorical variables. P<0.05 will be considered significant. STATA 15.1 will be used for the analysis.

12- Source of funding: (Please include source of funding even if self funding)

- Faculty of Medicine, Cairo University

Cairo University

KASR ALAINY

CAIRO UNIVERSITY - FACULTY OF MEDICINE

- Other sources:

Please specify: self funding

13- Time plan:

- When to start?
Just after thesis registration
- When expected to finish?
within 6 months or as soon as number of participants has been reached.
- When to publish? As soon as results are available.

14- References:

1. Jafarinab, M. R., Feizi, S., Baghi, A. R., Ziae, H., & Yaseri, M. (2010). Aspheric versus spherical posterior chamber intraocular lenses. *Journal of ophthalmic & vision research*, 5(4), 217.
2. Unsal, U., & Sabur, H. (2020). Comparison of new monofocal innovative and standard monofocal intraocular lens after phacoemulsification. *International Ophthalmology*, 1-10.
3. de Silva, S. R., Evans, J. R., Kirthi, V., Ziae, M., & Leyland, M. (2016). Multifocal versus monofocal intraocular lenses after cataract extraction. *Cochrane Database of Systematic Reviews*, (12).

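### The unit of analysis is not stated: if monocular acuity is t-tested as 20 versus 20 independent eyes, the 5% error rate for best-corrected acuity becomes about 9–17% at assumed between-eye correlations of 0.3–0.9.

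*Combined protocol and SAP*

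**What the plan says.** Under Methodology in details (section 7), "40 eyes of 20 patients will be included in this prospective study". Each group has 10 patients and 20 eyes, and a patient receives the same lens in both eyes.

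Under Follow up, the three-month assessment covers "Corrected and uncorrected distance (at 6 meters) and intermediate (at 66cm) vision both unocular and binocular". Section 9 makes uncorrected and best-corrected distance and intermediate acuity primary, without saying whether the monocular or the binocular value is meant.

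Section 10 reads "With a sample size of 18 (9/group), we will have a power of 95" per cent. It assumes mean uncorrected intermediate acuity (UIVA) of 0.16 and 0.27 logMAR, each with SD 0.06. It does not say whether the nine are eyes or patients, or at which level the SD applies.

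Section 11 says "Comparison between the two groups will be done using the Students t test or the Wilcoxon rank sign test according to data normality". It has no rule for averaging eyes or choosing one eye, and no mixed model or clustered standard error.

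The Preoperative assessment text adds a feature that matters for uncorrected acuity: "While in the Tecnis group the dominant eye will be aimed at 0 D and the non-dominant eye for -0.5 D".

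**The concern.** The lens is assigned by patient, so the trial has 20 independent units, not 40. Two eyes of one person share age, surgeon, setting and testing conditions, and their acuities would be expected to correlate. A two-sample t test on 40 eyes counts each patient twice. With positive correlation its standard error is too small, and chance differences between the lenses are declared significant too often.

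The plan does not commit to this analysis, but nothing in it rules it out. An eye-level and a patient-level analysis would both comply with section 11, so the choice could be made after the data are seen. A reader could not tell which one lies behind a reported P value. Monocular acuity is within the primary set as written, so the gap reaches the main results.

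**Working it through.** **Inputs from the protocol.** 10 patients × 2 eyes per group (section 7); UIVA means 0.16 and 0.27, so the difference is 0.11; SD 0.06; significance level 0.05 (sections 10 and 11). Sidedness is not stated; two-sided is used here.

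**Assumed inputs.** Between-eye correlation ρ from 0.1 to 0.9. For uncorrected acuity, a shift of 0.05 or 0.10 logMAR between the two eyes of a control patient and none in the other group. The documents give none of these values.

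**Step 1: the plan's own figure.** For a two-sample t test, the noncentrality is (0.11/0.06) × √(n/2). At n = 9 this is 1.833 × 2.121 = 3.89 on 16 df, giving 95.4% power. The stated 95% is reproduced.

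**Step 2: why the eye-level test goes wrong.** In SD units, the true variance of a group mean is (1+ρ)/20. The t test estimates it as s²/20. Within a group the expected s² is [9(1+ρ) + 10(1−ρ)]/19 = 1 − ρ/19. The ratio of true to estimated variance is therefore about (1+ρ)/(1 − ρ/19). At ρ = 0.9 this is 1.9/0.953 = 1.99: the variance is understated by about half. The effective number of eyes per group is 20/(1+ρ).

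**Step 3: best-corrected acuity (no shift).** 200,000 null trials per scenario, eye-level t test on 38 df:

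| ρ | Effective eyes per group | Type I error, eye-level t test |
|---|---|---|
| 0 (check) | 20 | 5.0% |
| 0.1 | 18.2 | 6.1% |
| 0.3 | 15.4 | 8.7% |
| 0.5 | 13.3 | 11.4% |
| 0.7 | 11.8 | 14.0% |
| 0.9 | 10.5 | 16.8% |

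Repeat simulations differ by a few tenths of a point (16.4% to 16.8% at ρ = 0.9). The large-sample formula 2[1 − Φ(1.96/√(1+ρ))] gives 8.6% at 0.3 and 15.5% at 0.9. It is lower at the top end because it ignores the small-sample behaviour of s². A rank-sum test on eyes gives about 8.2% and 16.1%, so the non-parametric fallback does not cure the problem.

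**Step 4: uncorrected acuity (control-arm shift).** A systematic difference between a control patient's eyes inflates s² without changing the sampling error of the group mean. A shift of f SDs adds 5f²/19 to s² in the control arm, or half of that to the pooled variance. For 0.10 logMAR, f = 0.10/0.06 = 1.67, and the pooled addition is 5 × 2.78/38 = 0.37. This offsets some or all of the understatement:

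| Shift (logMAR) | ρ = 0.3 | 0.5 | 0.7 | 0.9 |
|---|---|---|---|---|
| 0.05 | 7.3% | 9.7% | 12.1% | 14.5% |
| 0.10 | 4.4% | 6.3% | 8.1% | 10.1% |

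At ρ = 0.1 with a 0.10 shift the test is conservative (2.9%).

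**Step 5: one value per patient.** A t test on the mean of the two eyes (10 versus 10, 18 df) has type I error of 4.9–5.1% in every scenario.

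**Step 6: power after the change.** If SD 0.06 is per patient, the noncentrality at n = 10 is 1.833 × 2.236 = 4.10, and power is 97.2%. If it is per eye, the SD of a patient mean is 0.06 × √((1+ρ)/2). That is 0.048 at ρ = 0.3 (power 99.8%) and 0.058 at ρ = 0.9 (power 97.8%).

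**The case against.** The best defence is that the plan probably means patients. The heading of section 10 asks for study subjects, nine per group fits ten recruited patients with one spare, and the objectives compare patient groups. If nine meant eyes, 20 eyes per group would be more than twice what was needed. That makes a patient-level sample size plausible. It does not say how two monocular values become one, and section 7 also counts the groups in eyes.

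Two further points stand as limits:

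- The 9–17% range does not apply to UIVA, the only outcome that was powered. There the error may be smaller or even conservative, and the calculation assumes no between-eye shift in the Eyhance group, whose target is given as a choice of two values.
- If the planning assumptions are right, the UIVA difference is large enough to be detected on either unit. The practical risk is greatest for best-corrected distance and intermediate acuity, which are also primary and for which no expected difference is given.

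Outcomes with one value per patient are not in question: binocular acuity, the defocus curve ("Mean binocular defocus results will be measured and defocus curves of the two lenses will be created") and the questionnaire ("A questionnaire to evaluate the photic phenomena and spectacle independence will be explained and filled by the patients"). Contrast sensitivity is affected only if tested eye by eye, which the plan does not say.

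**Conclusion.** The concern holds and should be fixed before analysis. The plan collects paired-eye data for primary outcomes and names a test that is valid only for independent observations, with no rule linking the two.

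If that test is applied to 20 versus 20 eyes, the error rate for monocular best-corrected acuity is 6.1% to 16.8% at correlations of 0.1 to 0.9, or 1.2 to 3.4 times nominal. For monocular uncorrected acuity it lies between 2.9% and 14.5% over the scenarios tabulated and noted above, so the direction cannot be predicted. All of these figures depend on an eye-level test being run and on assumed correlations and shifts. The problem is validity of the test, not lack of power.

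**What to change.** In sections 9 to 11:

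- State that the patient is the unit of analysis (10 versus 10), that nine per group means patients, and whether SD 0.06 is per eye or per patient.
- State whether the monocular or the binocular value is primary for each acuity measure. Analyse binocular outcomes on the single binocular value.
- For monocular outcomes, analyse the mean of the patient's two eyes. The alternative is a mixed model with a patient random intercept and small-sample degrees of freedom. For uncorrected acuity that model needs a dominant/non-dominant eye by group term, and the plan should define the lens effect as the group difference averaged over both eye types. Otherwise the group coefficient may describe one eye type only.
- Note that for uncorrected acuity the two-eye mean compares each lens together with its refractive targets, since the control arm averages two different targets.
- State whether contrast sensitivity is monocular or binocular.

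The cost is a few lines of text, with no new data and no more patients. With positive correlation, P values for monocular best-corrected acuity will usually be less favourable than from an eye-level test. For uncorrected acuity they could move either way.

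### The plan does not show that its SD of 0.06 logMAR, on which the sample size rests, applies to intermediate acuity read on a Jaeger chart; a letter-scored logMAR chart at 66 cm is a cheap improvement

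*Combined protocol and SAP*

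**What the plan says.** Section 10 (Sample size) rests on UIVA alone. It asks whether "mean logMAR For UIVA is significantly lower in the new monofocal IOL (~0.16 +/-0.06") than in the "standard monofocal IOL with a mean logMAR for UIVA Of ~0.27 (0.06"), "using a 2 samples means test and a significance level of 0.05". The result is "With a sample size of 18 (9/group), we will have a power of 95" per cent. The source of the SD and the chart behind it are not given.

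Section 7 (Study Methods, Follow up) assigns the ETDRS chart to distance acuity and reads "intermediate and near visual acuity by Jaeger chart at 66 cm and 33 cm respectively". It adds: "Measured values of the visual acuity will be expressed in decimal values and will be converted to logMAR values". It gives no Jaeger line spacing, scoring rule or conversion for 66 cm. Acuity is taken in each eye and binocularly, and the reading that carries the powered comparison is not named.

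Planned enrolment is slightly above the calculated size: "40 eyes of 20 patients will be included in this prospective study", that is, 10 patients and 20 eyes per group.

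**The concern.** The calculation treats UIVA as a continuous logMAR measurement with a small SD. A chart read by print size returns only the values of its lines. If those lines are widely spaced relative to 0.06, reading in steps adds variance. It also leaves few distinct values in a group of 9 or 10, and the observed mean difference then depends partly on where the lines fall relative to the two means. The expected difference is 0.11 logMAR, about one step if lines are 0.10 apart and about half a step if they are 0.20 apart.

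The conversion matters too. The same print at 33 cm and 66 cm differs by log10(66/33) = 0.30 logMAR, so a distance-specific conversion is needed and none is given. A constant error would cancel between the groups, but the observed means could then not be compared with the planning values.

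Resolution lost when the chart is read cannot be restored in the analysis, so the choice has to be settled before data collection.

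**Working it through.** **Inputs.** From section 10: means 0.16 and 0.27 (difference 0.11), SD 0.06, 9 per group, significance level 0.05. From section 7: 10 patients per group. Sidedness is not stated; a two-sided test is taken because it reproduces the plan's figure. The step size h is an assumption, shown as a range.

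**1. The plan's own figure.** For a two-sample t test the noncentrality is 0.11 / (SD × √(2/n)).
- n = 9: 0.11 / (0.06 × √(2/9)) = 3.89, 16 df, critical value 2.12, power 95.4%. The stated 95% is reproduced.
- n = 10: 0.11 / (0.06 × √(2/10)) = 4.10, 18 df, critical value 2.10, power 97.2%.

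**2. Adding reading steps, if 0.06 contains none.** With equal steps h, the rounding SD is h/√12 and the total SD is √(0.06² + h²/12). For h = 0.10 this is √(0.0036 + 0.00083) = 0.0666. The power formula of step 1 is then re-used. As a check, trials were simulated with normal UIVA, readings rounded up to the next line, line positions varied and one reading per patient.

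| Step h (logMAR) | Rounding SD | Total SD | 9/group: formula; simulation | 10/group: formula; simulation |
|---|---|---|---|---|
| none | 0 | 0.060 | 95.4%; 95% | 97.2%; 97% |
| 0.10 | 0.029 | 0.067 | 90.8%; 91% | 93.7%; 94% |
| 0.15 | 0.043 | 0.074 | 84.1%; 85% | 88.1%; 87% |
| 0.20 | 0.058 | 0.083 | 74.9%; 73% | 79.8%; 77% |

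At h = 0.20 the simulated power depends on where the lines fall: about 57% to 84% at 9 per group and about 64% to 87% at 10. By the formula, 10 per group stays at or above 95% up to h of about 0.08, 90% up to about 0.14 and 80% up to about 0.20. Regaining 95% would take 11, 13 or 16 per group at h = 0.10, 0.15 or 0.20.

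**3. If 0.06 already includes the reading error.** The underlying SD is then √(0.06² − h²/12): 0.053 at h = 0.10 and 0.042 at h = 0.15. Simulated power is about 95–96% (9 per group) and 97% (10) at 0.10, and 94% and 96% at 0.15.

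**4. Both eyes averaged, 10 patients per group.** With an assumed fellow-eye correlation r, the total SD of step 2 is multiplied by √((1 + r)/2). For r from 0.8 to 0.5, power is 95.7% to 98.1% at h = 0.10, 91.2% to 95.2% at 0.15 and 83.8% to 89.7% at 0.20.

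**5. Decimal recording.** Converting decimal to logMAR is one-to-one. With decimals kept to 0.01, simulated power is unchanged (95% at 9 per group, 97% at 10). If they were rounded to 0.1, it would be 93% and 95.5%. The plan does not state the rounding.

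**The case against.** The strongest reply is that the step size, on which everything depends, is not in the documents. A reader might infer that the stated 95% is wrong, or that the trial will be underpowered. The documents do not support either. The 95% follows from its inputs, and an observed SD of 0.06 from a similarly graded chart would already contain the reading error, so adding it again would count it twice (step 3). This part of the reply stands.

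Two further inferences also go too far. One is that rounding noise is about as large as the assumed SD. That is true only near 0.20 steps; at 0.10 it is about half. The other is that passing through decimals loses resolution. It does so only if the decimals are rounded coarsely, which the plan does not say.

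It can also be said that 10 patients per group, not 9, are planned, and that a second eye is available. Both are correct and both soften the result. However, section 11 does not name the unit of analysis, so the gain from averaging eyes is possible rather than planned.

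Finally, section 7 records that the ETDRS chart is not available at Kasr Alainy hospitals, and the plan does not say that distance acuity is scored letter by letter. The fix must therefore state the scoring rule, and its cost is a judgement rather than a documented figure. What the reply does not remove is that the powered outcome is read on a chart with no stated grading or conversion, and its assumed SD is not tied to that chart.

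**Conclusion.** The point holds as a gap in justification and a worthwhile improvement in measurement, not as a demonstrated loss of power. The plan does not show that SD 0.06 applies to Jaeger readings at 66 cm converted to logMAR.

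At the planned 10 patients per group the consequence ranges from nothing to a fall from about 97% to 77–80%. The lower end needs three conditions together: steps of 0.20 logMAR, an SD of 0.06 free of reading error, and one reading per patient. At 0.10 steps the loss is modest (93–94%), and at 0.15 power is 87–88%. Unequal Jaeger steps would change these figures; equal steps are a simplification. The change is recommended because it is cheap and gives a finer reading of the one outcome the trial is sized on.

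**What to change.** In section 7, specify that intermediate acuity is measured at 66 cm on an ETDRS-format logMAR chart scaled for that distance and scored letter by letter. Enter logMAR directly for distance and intermediate acuity instead of converting from decimals. Keep the Jaeger chart for the 33 cm reading only.

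If Jaeger is kept at 66 cm, state its line steps, the scoring rule and the conversion to logMAR at that distance, justify the SD for that instrument, and restate the power in section 10. In either case, name the reading (monocular or binocular) and the unit of analysis that the power refers to.

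The cost is obtaining one chart, a wording change, slightly longer testing, and results that compare less directly with Jaeger-based reports.

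### Section 9 lists several acuities as joint primary outcomes without designating UIVA, the only one powered, and the plan has no testing order, success rule or named primary viewing condition

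*Combined protocol and SAP*

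**What the plan says.** - **Section 9 (Study outcomes), primary outcomes:** "Uncorrected and best-corrected distance, and intermediate visual acuity". No ranking is given and no acuity is designated as the lead.
- **Section 5 (Objectives), objective 1:** "Comparison of uncorrected and best corrected distance and intermediate vision in patients". This crosses two corrections with two distances, giving four acuities.
- **Section 7 (Study Methods), Follow up, three-month visit:** "Corrected and uncorrected distance (at 6 meters) and intermediate (at 66cm) vision both unocular and binocular". Both viewing conditions are recorded; neither is called primary.
- **Section 7, Methodology in details:** "40 eyes of 20 patients will be included in this prospective study", that is, 10 patients and 20 eyes per lens.
- **Section 10 (Sample size):** 9 per group gives "power of 95% to assess whether the mean logMAR For UIVA is significantly lower in the new monofocal IOL", with means of about 0.16 and 0.27 logMAR and SD 0.06 in each group, "using a 2 samples means test and a significance level of 0.05". No other acuity is powered, and the viewing condition behind these figures is not given.
- **Section 11 (Statistical analysis):** "Comparison between the two groups will be done using the Students t test", or a rank test if the data are not normal, and "P<0.05 will be considered significant". There is no adjustment, no testing order, and no statement of which result, or how many, would count as success.

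**The concern.** Sections 9 and 10 point to different primary outcomes. Section 10 implies that the trial is about UIVA. Section 9 gives distance acuity and best-corrected intermediate acuity the same standing. With one unadjusted threshold for every test, the report could rest on whichever primary acuity reached significance, and the plan would not contradict it.

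The unnamed viewing condition adds a second free choice. Unocular and binocular UIVA are different quantities. Unocular data also give two correlated eyes per patient, whereas the section 10 calculation counts independent observations. If the condition is chosen after the data are seen, the link between the analysed outcome and the power calculation is lost.

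At stake is whether a positive finding from 10 patients per lens can be taken at its nominal error rate. That matters because the background section says the results may influence the choice of lens.

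**Working it through.** **1. The plan's own figure.** Inputs from section 10: difference 0.27 − 0.16 = 0.11 logMAR, SD 0.06, alpha 0.05. Sidedness is not stated; two-sided is used here and reproduces the figure. The method is a two-sample t test with noncentral t power.

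Standard error = SD × √(2/n); noncentrality = 0.11 / standard error.

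| n per group | Standard error | Noncentrality | df | Critical t | Power |
|---|---|---|---|---|---|
| 8 | 0.0300 | 3.667 | 14 | 2.145 | 92.6% |
| 9 | 0.0283 | 3.889 | 16 | 2.120 | 95.4% |
| 10 (planned) | 0.0268 | 4.099 | 18 | 2.101 | 97.2% |

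Nine per group is the smallest number reaching 95%, so section 10 reproduces for UIVA tested alone.

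**2. How many primaries.** Objective 1 and the follow-up list both support 2 corrections × 2 distances = 4. The comma in section 9 would allow three (uncorrected distance, best-corrected distance, intermediate).

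**3. False positives if any one significant primary counted.** This is a conditional calculation, because the plan has no such rule. Assumptions: no true difference on any acuity, 10 independent patients per group, normal outcomes, and a common correlation between the four acuities (assumed; the documents give none).

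Independent tests, exact:
- either direction: 1 − 0.95⁴ = 0.185
- favouring the new lens only: 1 − 0.975⁴ = 0.096

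Correlated tests, simulated (400,000 replicates of four t tests, 10 against 10):

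| Assumed correlation | Favouring new lens (nominal 2.5%) | Either direction (nominal 5%) |
|---|---|---|
| 0 (exact) | 9.6% | 18.5% |
| 0.5 | 7.9% | about 16% |
| 0.8 | 5.9% | about 12% |
| 0.9 | 4.8% | about 10% |

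The first column of results is the more relevant, since section 10 frames a claim in favour of the new lens. On the three-acuity reading with independent tests, the either-direction figure is 1 − 0.95³ = 14.3%.

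**4. If all four had to be significant.** The false-positive rate is not inflated. However, the background section expects distance image quality with the new lens to be on a par with aspheric monofocal lenses. If distance acuity truly does not differ, each distance test reaches two-sided significance only about 5% of the time, so the joint power is at most about 5%. This rule is not workable as a superiority criterion.

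**5. UIVA power under each repair, at the planned 10 per group.**
- UIVA as single primary, alpha 0.05: 97.2%.
- Fixed testing order with UIVA first, alpha 0.05 for UIVA: 97.2%.
- Bonferroni over four, alpha 0.05/4 = 0.0125, critical t 2.775: 89.2%. Reaching 95% would need 12 per group.

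**The case against.** The strongest reply is that section 10 already shows the intention. It powers one directional claim on UIVA, and the background expects intermediate vision to improve while distance quality is maintained. On that view no one would treat a chance difference in distance acuity as success, and a result favouring the standard lens would certainly not count. The study is also a small master's project that describes itself as a case series, so a formal success rule carries less weight than in a confirmatory trial.

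Part of this stands. It is why the one-direction figures come first and why the inflation is stated as conditional. It does not close the gap: section 9 is where the primary outcome is defined, and an intention inferred from a sample size section does not bind the report.

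Four stronger readings are tempting, and the documents do not support them:
- *The trial's error rate is 18.5%.* That needs an any-one-counts rule, fully independent acuities and results counted in both directions. The plan states no such rule, and acuities measured in the same patients are likely to be correlated.
- *The sample size is wrong.* It reproduces for UIVA.
- *The viewing condition is never stated.* Both conditions, the test distances and the three-month visit are all given. What is missing is which condition is primary.
- *Power falls if the section 10 inputs describe the other condition.* The documents give no figures for a second condition, and power could move either way. With an assumed SD of 0.05, for example, it would be 99.6% at 10 per group.

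**Conclusion.** The point holds as a gap in pre-specification. Four acuities (three on the narrowest reading of the comma) share primary status, only UIVA is powered, and nothing says how the results combine or which viewing condition decides. Under an any-one-counts reading, the false-positive rate favouring the new lens would be roughly two to four times its nominal 2.5%. The multiple depends on the assumed correlation, on no true difference anywhere, and on one independent value per patient. Under an all-four reading error is controlled, but the criterion could hardly be met. Neither reading gives an interpretable trial; a designated UIVA does, at 97.2% power with the planned 20 patients if the section 10 inputs apply to the chosen viewing condition. The repair should be made, and it does not call the section 10 arithmetic into question.

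**What to change.** **Section 9.** Name UIVA at 66 cm and 3 months, in one pre-stated viewing condition and with one value per patient, as the single primary outcome, tested at two-sided 0.05. If the condition is unocular, also state in advance how the single value per patient is obtained. Move the other three acuities to secondary and report them as between-group differences with 95% confidence intervals.

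**Alternative.** Keep all four as primary in a fixed testing order with UIVA first, each tested at 0.05 only if the one before it is significant. UIVA keeps 97.2% power. Bonferroni over four is also valid but lowers it to 89.2%.

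**Section 11.** State the chosen rule, so that the 0.05 threshold no longer applies to every primary comparison without order or adjustment.

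**Section 10.** Add one clause confirming that its means and SDs refer to the chosen viewing condition. If they do not, restate the inputs and the power.

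**Cost.** Wording in three sections. No added patients or measurements are needed if the section 10 inputs match the chosen condition; otherwise the sample size calculation has to be redone. The downside is that the other acuities lose the primary label or, under the fixed order, are tested only after UIVA.
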